3.3.4.7. Study Deviations

Every attempt must be made to avoid deviations. All deviations are recorded on a Protocol Deviation Case Report Folio. United States regulations (21 CFR 812.140) require that investigators maintain accurate, complete, and current records relating to the clinical study. This includes documents showing the dates and reasons for each deviation from the clinical investigational plan. Protocol deviations will be reported to the Institutional Review Board (IRB) in accordance with IRB policies and/or local laws. All deviations will be summarized and reported in regular progress reports to the FDA.

3.3.4.8. Adverse Events

Any adverse experiences reported by a subject in the study or noted by the Clinical Investigator/Sponsor, will be reported on the Post-Operative Assessment CRF. Each experience must be categorized by the Clinical Investigator/Sponsor by its degree of severity (mild - the event did not require treatment, moderate - the event was treated locally or by minimally invasive treatment, or severe - the event was fatal or resulted in permanent injury or disability), its relationship to study device and implantation procedure (not related, associated with, caused by), and whether or not the adverse experience was unanticipated. An unanticipated adverse effect as defined by the FDA is any serious adverse effect on the health and safety or any life-threatening problem or death caused by, or associated with, a device, if that effect, problem or death was not previously identified in nature, severity or degree of incidence in the investigational plan or application (including a

supplementary plan or application), or any other unanticipated serious problem associated with a device that relates to the rights, safety or welfare of subjects (Section 812.3). Refer to Appendix 2, Instructions for Use and the Study Subject Informed Consent (Appendix 4) for a listing of known events.

Adverse events are to be scored as follows:

0 = None; the event was not observed

1 = Mild; the event was observed, but no treatment was required or the event resolved without treatment

2 = Moderate; the event was treated locally or by minimally invasive means

3 = Severe/Serious; as defined below

All events scored as "3" or "severe" are considered serious adverse events (SAES) under the regulatory definition in 21 CFR 803. These events will be reported within five working days to FDA. Specifically, serious illness or injury is one that is:

- Life-threatening (or fatal),
- Results in permanent impairment of a body function or permanent damage to a body structure; or
- Necessitates medical or surgical intervention to preclude permanent impairment of a body function or permanent damage to a body structure.

The Clinical Investigator/Sponsor will report all unanticipated, device deterioration events to the FDA.

Historical data have demonstrated that several types of complications are known to occur with this procedure. These complications are described in the following sections.

Endoleaks

Immediately after placement of the Medtronic Thoracic Stent Graft System, or upon later evaluation, endoleaks may be detected. Endoleaks are considered any extravasation of contrast outside of the flow channel established by the stent-graft. For purposes of this study, endoleaks that are detected and corrected during the implantation procedure are not considered a complication of the device or procedure. However, uncorrected endoleaks that develop during implantation or endoleaks that develop after implantation are considered complications and must be reported on the Procedure or Post-Operative Assessment CRF. The type and possible cause of the endoleak should be noted on the CRF.

Table 2: Endoleak Type and Causes

Endoleak Type	Description	Probable Cause(s)	Relationship to Device
I	Attachment endoleaks (distal or proximal)	Improper graft sizing or vessel measurement	Device-related
II	Branch flow endoleaks	Inadequate identification of feeder vessels and/or graft placement	Not device-related
III	Mid-graft or modular endoleaks	Graft tears or punctures, improper docking of sections	Device-related
IV	Fabric porosity	Fabric defect	Device-related

Treatment of endoleaks is at the discretion of the Clinical Investigator/Sponsor. In general, it is recommended that endoleaks be corrected during the initial procedure unless the Clinical Investigator believes that there is a likelihood that the endoleak may spontaneously seal after a few days. The decision to intervene at later intervals will be based on the severity of the endoleak, the possible cause of the endoleak, the status of the aneurysm, and the subject's general health. Known or suspected endoleaks must be monitored carefully postoperatively with appropriate diagnostic imaging.

Attempts to correct postoperative endoleaks may be done by any of the following procedures:

- using an endovascular balloon to remodel the stent-graft near the endoleak;
- use an endovascular methodology to seal the leak;
- implanting an extension cuff over the endoleak; or surgical intervention.

Any procedure performed to correct postoperative endoleaks will be recorded on the Post-Operative Assessment CRF.

Conversion to Surgery

In some subjects there may be difficulty inserting and implanting the Medtronic Thoracic Stent Graft System during the procedure. If it is not possible to complete implantation of the device, or if peri- or post-operative complications arise that place the subject at risk, the Clinical Investigator/Sponsor may elect to convert the patient to open surgery. Alternatively, the Clinical Investigator/Sponsor may elect not to repair the dissection/hematoma, and to manage the patient with observation only. This is especially true for patients who are deemed not operative candidates. In such cases, the reason for conversion must be recorded on the Procedure CRF.

Also, as noted previously, subjects who convert to surgery or who are managed by observation will be followed in an identical manner as the other subjects. A Post- Operative Assessment CRF will be completed at 1, 6, and 12 months after the attempted implantation.

Death

Autopsies will be requested for subjects who expire following implantation of a Medtronic Thoracic Stent Graft System. If the patient or the family consents to a post- mortem exam, the device will be explanted whenever possible for examination and histological analysis. The Clinical Investigator/Sponsor will request that the explanted device be sent to the designated facility for examination and histological analysis. The Clinical Investigator/Sponsor will determine whether or not the device (or procedure) caused or contributed to the subject's death.

Other Adverse Events

The health risks associated with use of the Medtronic Thoracic Stent Graft System may be less than for conventional surgical treatment. However, as with any medical procedure, there are some risks. There is the potential for discomfort or complications resulting from the procedure and the implanted stent graft. It is hypothesized that the rate of serious adverse events in stent-graft patients will be less as compared to an expected serious adverse event rate for surgical patients.

The following is a non-exhaustive list of potential serious complications that may occur during or following implantation of the Medtronic Thoracic Stent Graft System:

- embolization that may lead to stroke, amputation, intestinal ischemia, multiple organ failure, or death;
- renal insufficiency or failure, that may necessitate dialysis;
- unsuccessful repair or early endoleak, possibly leading to rupture of the aorta and death;
- propagation of dissection into the aortic root, possibly causing acute aortic regurgitation, or coronary dissection/occlusion, both leading to shock, conversion to surgery, or death;
- delayed endoleak, possibly leading to rupture of the lesion and death;
- vessel rupture, possibly leading to shock, conversion to surgery, or death;
- migration of the device, possibly leading to rupture of the aorta, open surgery, or death;
- blood loss, possibly leading to shock or death;
- graft twisting or kinking, possibly leading to shock or death;
- infection, possibly leading to septicemia or death;
- occlusion of blood flow to the spinal cord, possibly leading to temporary or permanent paraparesis or paraplegia;

- conversion to open surgery with all the risks associated with an open surgical repair;
- myocardial infarction, arrhythmia and/or congestive heart failure possibly leading to shock or death;
- respiratory failure possibly leading to death;
- cardiac injury including perforation due to nose cone introduction;
- deformation of the sinotubular junction causing aortic valve regurgitation;
- involuntary coverage of coronaries or brachiocephalic vessel (e.g. stent graft mal deployment and/or malposition).

Similarly, there are a number of minor risks and discomforts that could result from the implant procedure or adjunctive tests/analyses. The following is a summary of those potential discomforts.

- Heart and lung testing may involve some discomfort.
- Blood collection may cause bruising and/or discomfort.
- The CT and angiography procedures may cause discomfort during scanning, but should not cause pain.
- The radiopaque dyes used during CT and angiography procedures can cause nausea, vomiting, or other reactions.
- Some pain and bruising at the site may result in the groin where the device is inserted.

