1. Investigators are all chosen based on experience and skills in using endoluminal aortic devices. The study site at The Heart Hospital Baylor Plano is experienced with conducting investigational and feasibility studies in endovascular procedures. In case the patient population would need open surgical conversion, the investigators will be able to offer this life-saving measure promptly. The Heart Hospital Baylor Plano has an active open-heart surgery program.
2. Appropriate risk minimization activities were performed during the development and design verification tests of the device by Medtronic Vascular.
3. Adequate informed consent will be performed by explaining to the patients the endovascular, open surgical and medical treatment options.
4. Adherence to eligibility criteria and screening procedures will ensure that appropriate patients are enrolled. Screening procedures include careful history and thorough physical examination. Only patients that meet the aforementioned inclusion criteria will be entered in the study.
5. Adherence to the Medtronic Instructions for Use packaged with the Valiant Captivia PS-IDE device (Appendix 2) and the Valiant Navion device (Appendix 14).
6. By limiting the sample size to 5 patients at a time, the investigators appropriately mitigate the risks potentially associated with an early feasibility study.
7. The subjects will be carefully and regularly monitored throughout the study period. These follow-up intervals are more frequent than the follow-up offered to patients undergoing open repair, traditional feasibility or pivotal study).

8. The investigators will evaluate the subject adverse events during the course of the study and report these on timely and periodic fashion after completion of first five subjects or within three months, whichever is the shortest interval. All serious/severe adverse events will be reported within five working days to the FDA.
9. The device performance parameters will be reported in a timely and periodic fashion which helps to determine whether the stent graft design functions as intended.
10. This ascending stent graft is used in subjects with more favorable anatomical characteristics as compared to the population enrolled with descending thoracic pathologies. The investigators expect the aortic pathologies included in this feasibility study to have a more favorable exclusion rate by TEVAR compared to cohort with ascending aortic aneurysm.

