5.2. Name and Address of Monitor

Monitoring functions will be conducted by [name], Baylor Scott & White Research Institute, [name].

6. Oversight

The DSMB will be responsible for assuring that research subjects are not exposed to unnecessary or unreasonable risks. Ongoing responsibilities of the DSMB will be to evaluate the progress of the study, including periodic assessments of adverse events and serious adverse events. The DSMB will report on the safety and scientific progress of the study.

7. Additional records and reports

Case report forms should be entered into the electronic database within 10 days after the corresponding visit. Upon request of the reviewing IRB, DSMB, or FDA, the Baylor Scott & White The Heart Hospital - Plano will provide accurate, complete, and current information about any aspect of the study.

All Unanticipated Adverse events will be reported to the IRB and FDA within 10 days of notification of event. All other adverse events and study updates will be reported at the IRB continuing review as well as the FDA annual review.

The enrollment will be performed in five-patient increments, and the results of each five-patient group will be analyzed and reported prior to enrolling further patients.

Copies of the CRFs are in Appendix 3.

8. Investigator Information

8.1. Names and addresses of Sponsor-Investigator:

[name]
Baylor Scott & White The Heart Hospital - Plano
[name]
[name]

Co-Investigators

[name]
Baylor Scott & White The Heart Hospital - Plano
[name]
[name]

[name]
Baylor Scott & White The Heart Hospital - Plano
[name]
[name]

[name]
Baylor Scott & White The Heart Hospital - Plano

[name]
[name]

[name]
Baylor Scott & White The Heart Hospital - Plano
[name]
[name]

J. [name]
Baylor Scott & White The Heart Hospital - Plano
[name]
[name]

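### SAE status rests on a severity score whose categories overlap (3.3.4.8), and Section 7 contradicts the five-working-day FDA rule for serious events

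*Combined protocol and SAP*

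**What the plan says.** Section 3.3.4.8 grades adverse events twice.

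- **Narrative grading (opening paragraph).** The Clinical Investigator/Sponsor classes each event as mild, moderate or severe. Moderate is defined by local or minimally invasive treatment. The top category reads "or severe - the event was fatal or resulted in permanent injury or disability".
- **Numeric grading, 0 to 3.** The middle score is "2 = Moderate; the event was treated locally or by minimally invasive means". The top score is "3 = Severe/Serious; as defined below". The list below it has three criteria: life-threatening or fatal; permanent impairment or damage; and "Necessitates medical or surgical intervention to preclude permanent impairment of a body function or permanent damage to a body structure".

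Events that are scored 3 or called severe are the SAEs, and they go to the FDA within five working days. Section 3.4.2.1, item 8, repeats this: "All serious/severe adverse events will be reported within five working days to the FDA".

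Section 7 (Additional records and reports) sets a different schedule. Unanticipated events go to the IRB and FDA within 10 days. For the rest: "All other adverse events and study updates will be reported at the IRB continuing review as well as the FDA annual review". It makes no exception for serious events.

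**The concern.** Severity and seriousness are different attributes. Here seriousness is read off a severity score, and one level of that score is defined by treatment route. This is an endovascular study, and the protocol names catheter-based responses to several complications: balloon, cuff or other endovascular sealing for endoleak (3.3.4.8), endovascular repair as one option for vessel rupture (3.4.2.2, item 6), and stenting as one option for a covered coronary artery (3.4.2.2, item 17). Early endoleak, vessel rupture and coronary coverage also appear in the protocol's own list of potential serious complications (3.3.4.8). The same event can therefore satisfy two scores, only one of which makes it an SAE.

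What is at stake is the SAE tally and the speed of reporting. The DSMB periodically assesses adverse events and SAEs (Section 6). Enrolment proceeds in groups of five, with results reported before the next group (3.3.3, Section 7). The protocol also says "It is hypothesized that the rate of serious adverse events in stent-graft patients will be less", compared with the rate expected for surgical patients. If two readers can classify the same event differently, or follow different reporting clocks, these uses are weakened.

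**Working it through.** No arithmetic applies. The plan states no SAE rate, and the question is whether its rules agree. The check sets them side by side.

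**Step 1: classify one event under each rule.** Take a life-threatening complication that is treated by catheter and leaves no permanent injury.

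| Rule in 3.3.4.8 | Result | SAE? |
|---|---|---|
| Narrative grading | Moderate: minimally invasive treatment, not fatal, no permanent injury | No |
| Numeric score 2 | Met, by treatment route | No |
| Numeric score 3 | Met, as life-threatening | Yes |

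Nothing in 3.3.4.8 says that the higher score prevails, and the section names no independent adjudicator.

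**Step 2: change only the treatment route.** If the same complication is treated by open surgery and again leaves no permanent injury, score 2 no longer applies and score 3 is the only numeric score that fits. On the numeric scale, the route alone decides whether a non-serious score is available. The overlap can only take qualifying events out of the SAE count; it cannot add any.

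**Step 3: what the narrower wording does.** An event is an SAE if it is scored 3 *or* called severe. The narrower narrative wording therefore cannot cancel a score of 3. Its effect is indirect: it gives an assessor a textual reason not to assign 3 to an event that resolved.

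**Step 4: compare the reporting clocks.**

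| Serious event | Recipient | 3.3.4.8 and 3.4.2.1 item 8 | Section 7 |
|---|---|---|---|
| Anticipated | FDA | Five working days | Annual review |
| Anticipated | IRB | Not stated | Continuing review |
| Unanticipated | FDA | Five working days | 10 days |
| Unanticipated | IRB | Not stated | 10 days |

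For an anticipated serious event the two FDA rules can differ by up to about 12 months. For the IRB, Section 7 gives the only stated time. Death, stroke, vessel rupture, myocardial infarction and renal failure are already listed as known risks (3.3.4.8, 3.4.1). Read literally, Section 7 therefore puts many foreseeable serious events on the slow route, unless their nature, severity or frequency goes beyond what was listed. Section 5.1 has the monitor check that reporting is timely but gives no number of days.

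**Step 5: what is not affected.** Section 3.3.5.1 counts death, re-intervention, surgical conversion and stroke as primary endpoints. It counts endoleak, myocardial infarction, migration and malperfusion, among others, as secondary endpoints. None of these depends on the adverse-event score. The only formal test in the analysis section concerns 30-day mortality. One gap remains: re-intervention is not defined, so a rescue during the index procedure is not clearly counted there.

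**The case against.** The strongest reply is that a sensible investigator would read the rules correctly. Score 3 has no exception for minimally invasive treatment, so an event that meets the list is an SAE however it was treated. The five-working-day rule is stated twice and specifically for serious events, while the Section 7 sentence is a general residual clause that never mentions SAEs. The main clinical events are captured as endpoints anyway. The five-patient reviews look at results and adverse events generally, not only at an SAE count. The hypothesis about the SAE rate is one background sentence with no test or comparator in the analysis section. The CRFs are in an appendix that was not available, so a separate seriousness field may already exist.

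Much of this stands, and it rules out three stronger readings.

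- A reader might infer that any event fixed by minimally invasive means is non-serious. The numeric scale does not say so; it lets scores 2 and 3 both apply.
- A reader might infer that Section 7 settles the matter and defers SAEs to annual review. For the FDA it is one of two conflicting rules.
- A reader might take the 18.6% type I endoleak rate cited in Section 2.1.1, multiply by 20 patients to get 0.186 × 20 = 3.7, and call that the number misclassified. It is not. Only half of that review's patients had type A dissection. The documents do not say how many of the leaks were later corrected by catheter. Section 3.3.4.8 does not count leaks corrected during implantation as complications, and leaves later treatment, which may be surgical, to discretion.

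The reply does not remove the overlap without a precedence rule, the two definitions of severe, or the contradictory clocks. A seriousness field on the CRF would help, but the protocol text would still tie SAE status to the score.

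**Conclusion.** The point holds as an internal inconsistency with two parts. First, SAE classification in 3.3.4.8 is ambiguous for serious events treated endovascularly, so some could be scored 2 and left out of the SAE tally and expedited reporting. Second, Section 7 contradicts 3.3.4.8 and 3.4.2.1 on when serious events reach the FDA, and gives the IRB no expedited time for anticipated ones.

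That SAEs would in fact be undercounted or reported late is a risk, not a demonstrated result. Its size cannot be calculated, because the documents give neither the frequency of qualifying events nor the way assessors would resolve the overlap. The conclusion rests on the protocol text alone and assumes that no CRF instruction or other document supplies the missing precedence rule.

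**What to change.** - In 3.3.4.8, record seriousness as a separate yes/no item against the three criteria already listed, independent of severity score and treatment route. Define SAEs by that item.
- Keep a single definition of severe, and use it in both the narrative and the numeric grading.
- Reconcile Section 7 with 3.3.4.8 and 3.4.2.1: except SAEs from the clause on all other adverse events, and state one timeline per recipient (FDA and IRB), including for events that are both serious and unanticipated.

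The cost is protocol and CRF wording, possibly more expedited reports, and an SAE rate that may look less favourable. Sample size, endpoints and the mortality test do not change.

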2.1 Report of Prior Investigations (21 CFR 812.27)

2.1.1 Background

Cardiovascular disease management continues to develop gradually as its occurrence is a leading cause of death in many Western societies. There has been enhanced awareness of the spectrum of acute and chronic aortic syndromes due to improved diagnostic imaging modalities combined with longer life expectancy and exposure to high blood pressure. Vascular diseases of the aorta have been associated with very high mortality and morbidity. In the ascending aorta, the disease entails a variety of pathologies such as fusiform and saccular aneurysms, pseudoaneurysms, aortic transection, penetrating aortic ulcers, intramural hematoma, and acute and chronic aortic dissection. However, in the current iteration of this protocol we will only address dissections.

Aortic dissection involves a progressive tear in the aortic wall. The intima or inner lining of the aorta tears resulting in propagation of blood within the media or middle layer with multiple reentry sites, usually distally, but sometimes retrograde. Aortic dissections are classified as Stanford Type A or B depending on the location of the entry tear. Type A dissection starts in the ascending part of the aorta and usually expands to more distal portions of thoracic aorta. Type B dissection begins in the descending thoracic aorta and usually moves towards the abdominal aorta. In certain circumstances, Type B dissections can also propagate toward the heart.(ref #3) The standard treatment of thoracic aortic dissection has either been medical management or an open surgical procedure, depending upon the patient's clinical presentation. For patients with type A aortic dissection (involving the ascending aorta), surgical repair remains the gold standard as it offers significant survival advantage and improved quality of life. This entails heart-lung machine-assisted replacement of the ascending aorta (with or without aortic valve replacement). All of these operations require cardiac arrest and aortic cross-clamping with extracorporeal circulation. When the distal ascending aorta is involved, frequently the patients will require hypothermic circulatory arrest in order to replace the aortic arch. Due to the invasive nature of these operations and associated morbidity and mortality, they are offered only to about 50% of patients who are deemed reasonable operative risk, and average early (30-day) survival with surgical repair is 85%. (ref #4,5,6,7)

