3.3.4.6. CT/CTA Scan

Images of the CT without contrast and CTA (contrast enhanced CT) covering the length of the lesion, which may include scans of the chest, abdomen and pelvis will be submitted for evaluation through 60 months of follow-up. Images at pre-procedure, pre-discharge, 1 month, 6 months, 12 months, 24 months, 36 months, 48 months and 60 months will be evaluated. In addition, any interim imaging done within one year of implantation should be evaluated if it relates to the performance of the implanted device. These data will be used for analysis of secondary observations at pre-discharge, 1 month, 6 months and 12 months. Site data will be used for reporting purposes at 24 months, 36 months, 48 months and 60 months, and submitted for central review.

The presence of the following endpoint related events would be assessed:

- Loss of stent graft patency
- FL diameter over the length of the stented segment
- TL diameter over the length of the stented segment
- Total aortic diameter
- FL thrombosis
- Changes in true and false lumen volumes over time
- Stent graft migration
- Presence and type of endoleaks
- Continuing or new false lumen (FL) perfusion

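### The endoleak definition is not adapted to a dissection-only trial: false-lumen flow from uncovered distal re-entry tears can be recorded as an endoleak complication and has no type in Table 2

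*Combined protocol and SAP*

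**What the plan says.** Section 3.3.4.8 (Adverse Events, Endoleaks) gives one definition: "Endoleaks are considered any extravasation of contrast outside of the flow channel established by the stent-graft". Leaks corrected during the implant procedure are set aside, but "uncorrected endoleaks that develop during implantation or endoleaks that develop after implantation are considered complications" and have to be reported. The section adds: "The type and possible cause of the endoleak should be noted on the CRF".

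Table 2 in the same section offers four types: I (attachment site), II ("Branch flow endoleaks"), III (mid-graft or modular) and IV (fabric porosity). Types I, III and IV are classed as device-related and type II as not device-related.

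On the population, section 2.1.1 says that "in the current iteration of this protocol we will only address dissections" and describes dissection as "propagation of blood within the media or middle layer with multiple reentry sites, usually distally, but sometimes retrograde".

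Section 3.3.4.6 (CT/CTA Scan) lists the presence and type of endoleaks as one imaging finding and "Continuing or new false lumen (FL) perfusion" as another. Section 3.3.5.1 makes endoleaks a secondary endpoint; false-lumen perfusion is not in that list. Section 3.3.5.3 reports all secondary endpoints descriptively.

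**The concern.** The definition sets no limit on where the contrast comes from and makes no exception for the false lumen. That suits an aneurysm sac, and the section does speak of the aneurysm's status when discussing later intervention. It does not suit a dissection, where a second channel exists before treatment and may stay open beyond the graft.

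Under sections 3.1 and 3.2.2, treatment lies between the sinus of Valsalva and the innominate orifice. Ascending tears are covered, and in some retrograde cases the proximal descending tear as well. Tears further downstream are left uncovered by design. Contrast entering the false lumen through them lies outside the graft's channel although the graft has done its job.

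At stake is whether the endoleak percentage, a main measure of device performance here, separates loss of seal from residual distal flow. Results are also analysed after every five patients, and one reclassified patient moves a group's rate by 1/5 = 20 percentage points.

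**Working it through.** The documents give no expected endoleak rate and no calculation tied to this definition, so there is no plan figure to reproduce. The check has four steps.

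**1. Does re-entry flow meet the definition?** Take a patient whose ascending tear is fully covered and whose false lumen fills from a distal tear. The contrast is outside the channel formed by the graft, so the sentence in 3.3.4.8 is met on its literal reading. The word extravasation does not clearly rule this out, because type II (branch flow) is also flow that enters from elsewhere and not through the graft or its seals.

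**2. Does Table 2 have a place for it?** A distal re-entry tear is not an attachment site, a branch vessel, a graft defect or a fabric defect, so none of the four types fits. Table 3 gives some encouragement to choose a device-related type. For failure to exclude the false lumen it names acute type I and type III endoleak among the effects, and Table 2 classes both types as device-related. (Table 3 is footnoted as referring to the first-generation device only.)

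**3. Does it reach the formal test?** The only test is of 30-day mortality: the exact one-sided 95% upper limit must lie below 25%. For x deaths among n = 20, the limit is the 0.95 quantile of Beta(x + 1, 20 − x).

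| Deaths | Upper limit |
|---|---|
| 0 | 13.9% |
| 1 | 21.6% |
| 2 | 28.3% |

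The rule is met with at most one death. At a true rate of 25% that has probability 0.75^20 + 20 × 0.25 × 0.75^19 = 0.024. The endoleak count enters nowhere.

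**4. How far could the any-endoleak percentage move?** Let e be the true endoleak rate and r the share of patients with false-lumen flow from uncovered tears, all of it scored as endoleak. If the two are independent, the recorded rate is 1 − (1 − e)(1 − r). With full overlap it is max(e, r); with none it is e + r.

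- e = 18.6%, the type I rate in the systematic review cited in 2.1.1, used for illustration only. In 20 patients that is 0.186 × 20 = 3.7.
- r is not given in the documents. The range 10% to 75% is an assumption.

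| r (assumed) | Recorded rate, independent | Expected of 20 | Full overlap to no overlap |
|---|---|---|---|
| 10% | 1 − 0.814 × 0.90 = 26.7% | 5.3 | 18.6% to 28.6% |
| 25% | 1 − 0.814 × 0.75 = 39% | 7.8 | 25.0% to 43.6% |
| 50% | 1 − 0.814 × 0.50 = 59.3% | 11.9 | 50.0% to 68.6% |
| 75% | 1 − 0.814 × 0.25 = 80% | 15.9 | 75.0% to 93.6% |

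With e varied from 10% to 30% over the same r, the independent figure runs from 1 − 0.90 × 0.90 = 19.0% to 1 − 0.70 × 0.25 = 82.5%. If re-entry flow is kept out of the definition, the recorded rate returns to e.

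**The case against.** The strongest reply is that nobody would apply the sentence literally. Contrast in the coronaries or arch vessels is also outside the graft channel and would not be scored. The word extravasation, the demand for a type and cause, and the separate false-lumen item all point to a narrower meaning. This is one centre with central image analysis, and 3.3.4.8 separately grades each event's relationship to the device. The case report forms are not in the text available for review, so they may carry an option for other or unclear sources.

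Much of this is fair. It makes misclassification possible, not certain, but the narrower meaning is written nowhere. Nor does central reading settle it: 3.3.4.6 uses site data for reporting from 24 to 60 months, so a shared written rule is still needed.

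Four stronger readings are tempting and are not supported:

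- **An inflated device-failure rate.** No such rate is defined. The device-related count rises only if the flow is put into type I, III or IV.
- **Double-counting.** One finding can appear under two outcomes, but the two are never added or combined.
- **No comparison possible with the cited 18.6%.** Type is recorded, so a type I rate can be extracted. It is contaminated only by mis-typing.
- **A distorted primary endpoint through re-intervention.** Treatment of an endoleak is left to the investigator, so the definition alone creates no re-intervention.

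A last objection is that moving this flow to false-lumen perfusion takes it out of the listed secondary endpoints and out of the endoleak complication reports. That stands, and the fix has to deal with it.

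**Conclusion.** The concern holds as a fault in a stated rule: it is over-broad for this population, lacks a matching type, and overlaps another imaging item with no dividing line. The affected results are the descriptive any-endoleak percentage, the associated complication count and, only with mis-typing, the device-related count. The 30-day mortality conclusion does not change.

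The size cannot be determined from the documents. The 27% to 80% range depends on an assumed r, on independence, on every such case being scored as endoleak, and on an 18.6% input that is a type I rate from a review in which only half of the treated disease was type A dissection. It shows the sensitivity and is not an estimate: at r = 10% with full overlap there is no inflation at all. The point deserves correction because the ambiguity affects a device-performance outcome and costs little to remove.

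**What to change.** In 3.3.4.8, replace the definition with wording to this effect: an endoleak is persistent flow into the segment excluded by the graft, arising at an attachment site, from a branch of that segment, or through the graft or a junction (types I to IV). Add that opacification of the false lumen from an uncovered distal re-entry tear is recorded as false-lumen perfusion and not as an endoleak. Provide an indeterminate-source option on the form, and apply the same rule to site and central readings.

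In 3.3.5.1 and 3.3.5.3, report endoleaks by type, with indeterminate cases shown separately, and report false-lumen perfusion beside them at the same visits so that no finding drops out. This changes classification only; it does not touch how any leak is managed.

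The cost is a few sentences and one form option, plus re-classification of earlier scans from stored images. The downside is that readers must judge the source of flow, which will sometimes be impossible, for instance when a tear lies close to the distal edge of the graft.
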